3.4. Substudy procedures

3.4.1 Randomization

Eligible patients will be contacted via email to determine their interest in participation in the GAME PAD study. Patients will be randomized 3:1 to an email message framing trial participation in a standard opt-in manner versus an email message framing trial participation in an opt-out manner.

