3.4.4 Outcomes

For all outcomes, we will compare patients initially presented with study participation via opt-in framing versus opt-out framing. The primary outcome will be the proportion of patients that enroll in the study. Exploratory outcomes, among patients that ultimately enrolled in the study, will include the proportion of enrolled patients that failed to complete the study, change in daily step count from baseline to the end of the GAME PAD intervention and the end of follow-up (overall and stratified by overall GAME PAD study arm – gamification intervention versus attention control), and change in patient-reported symptom scores from baseline to the end of the GAME PAD intervention and the end of follow-up (overall and stratified by overall GAME PAD study arm)

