3.4.5 Informed consent

Because the trial tests different methods of approaching patients prior to enrollment, informed consent cannot feasibly be obtained and we will request a waiver of informed consent

4. Statistical Analysis

We will compare the primary outcome and attrition rate between patients initially presented with study participation via opt-in framing versus opt-out framing using the chi-square method. Change in step count from baseline through the intervention period and follow-up will be compared using paired t tests, as will change in patient reported symptom scores from baseline through the intervention period and the end of follow up. The primary outcome will be analyzed using the intention-to-treat principle, grouping patients by framing of study participation at initial contact. Other outcomes, among patients that ultimately enrolled in the GAME PAD study, will similarly group patients by framing of study participation at initial contact.

5. Human Research Protection

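### Paired t tests are named for comparing change in steps and symptom scores between two independent framing groups, so those exploratory comparisons have no valid test

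*Combined protocol and SAP*

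**What the plan says.** Section 3.4.4 (Outcomes) sets the contrast for the whole substudy: "For all outcomes, we will compare patients initially presented with study participation via opt-in framing versus opt-out framing". It then lists change in daily steps and change in symptom scores under "Exploratory outcomes, among patients that ultimately enrolled in the study". Each is measured to the end of the intervention and to the end of follow-up, and each is to be reported "overall and stratified by overall GAME PAD study arm – gamification intervention versus attention control".

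Section 3.4.1 (Randomization) describes how the groups arise: "Patients will be randomized 3:1 to an email message framing trial participation in a standard opt-in manner", with opt-out framing as the alternative. No matching or pairing of patients is described.

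Section 4 (Statistical Analysis) assigns the tests:

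- Primary outcome and attrition, a chi-square test: "We will compare the primary outcome and attrition rate between patients initially presented with study participation via opt-in framing versus opt-out framing using the chi-square".
- Steps: "Change in step count from baseline through the intervention period and follow-up will be compared using paired t tests".
- Symptom scores: "as will change in patient reported symptom scores from baseline through the intervention period and the end of follow up".

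The section ends by saying that the outcomes among enrollees "will similarly group patients by framing of study participation at initial contact". It names no two-sample test, regression or mixed model for steps or symptom scores.

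**The concern.** The contrast and the test do not match. A paired t test needs two measurements on the same unit, or on matched units. Opt-in and opt-out enrollees are separate, unmatched people, usually in unequal numbers, so nothing can be paired across framings. The pairs that do exist are baseline and later values in the same patient. A test on those asks whether one group's mean change is zero, not whether two groups changed by the same amount.

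An analyst following the text would produce one p-value for opt-in and one for opt-out, with no interval or test for the difference. A reader would then be tempted to infer a framing effect because one p-value is below 0.05 and the other is not. The plan does not state that rule, but it provides nothing in its place. An analyst who notices the problem would have to choose a replacement method, possibly after seeing the data.

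**Working it through.** The plan gives no sample size, SD, expected change or significance level for these outcomes, so there is no planned figure to reproduce. The defect follows from the text. The arithmetic below only illustrates its consequences.

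**1. Possible readings of the paired test**

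| Reading | Can it be computed? | Does it compare framings? |
|---|---|---|
| Pairs formed across opt-in and opt-out | No: no matching, and generally unequal numbers | – |
| Baseline vs later value within each framing group | Yes | No: it tests zero mean change in one group |
| A slip for a two-sample test on change | Yes, but it is not what is written | Yes |

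Only the third reading delivers the comparison in Section 3.4.4, and it requires the wording to be corrected.

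**2. Group sizes among enrollees**

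Inputs: 100 patients in the main trial (Section 3.1); 3:1 read as opt-in to opt-out (Section 3.4.1); enrollment rates in the two earlier trials described in Section 1. Opt-in share = 3·p_in / (3·p_in + p_out).

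- Diabetes trial, 13% vs 38%: 0.39/(0.39 + 0.38) = 50.6%, about 51/49.
- Myocardial infarction trial, 16% vs 38%: 0.48/(0.48 + 0.38) = 55.8%, about 56/44.
- No framing effect on enrollment: 75/25.

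**3. Contrasting the two within-group p-values**

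Assumptions: normal change scores, equal SD in both groups, two-sided 5% level, no missing data, and the *same* true change d (in SD units of change) in both groups. Let p1 and p2 be the power of the paired test in each group, from the non-central t distribution with n−1 degrees of freedom and non-centrality d√n. The probability that exactly one group is significant is p1(1−p2) + p2(1−p1).

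Examples at d = 0.3:

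- 51/49: p1 = 0.556 and p2 = 0.539, so 0.556×0.461 + 0.539×0.444 = 0.496.
- 75/25: p1 = 0.727 and p2 = 0.302, so 0.727×0.698 + 0.302×0.273 = 0.590.

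| True change in both groups (SD) | 0 | 0.1 | 0.2 | 0.3 | 0.4 | 0.5 | 0.6 |
|---|---|---|---|---|---|---|---|
| 51/49 | 9.5% | 19% | 41% | 50% | 33% | 12% | 3% |
| 75/25 | 9.5% | 19% | 43% | 59% | 51% | 33% | 18% |

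The 56/44 split is close to 51/49 (50% at d = 0.3, 13% at 0.5). In simulations with equal true change, a Welch test on the change scores rejected in 4.7% to 5.3% of runs in every setting.

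**4. Precision of a between-group comparison**

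Half-width of the 95% CI for the difference in mean change, in SD units: t(0.975, Welch df) × √(1/n1 + 1/n2).

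- 51/49: 1.985 × 0.200 = 0.40
- 75/25: 2.019 × 0.231 = 0.47 (with pooled df, 1.984 × 0.231 = 0.46)
- Within one GAME PAD arm, 26/24: 2.011 × 0.283 = 0.57
- Within one GAME PAD arm, 37/13: 2.079 × 0.322 = 0.67

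**The case against.** The affected outcomes are exploratory, and neither objective in Section 2 mentions steps or symptom scores. No main conclusion depends on the faulty sentence. This stands, and it limits how serious the point is.

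The word *paired* may be a slip. Section 4 also says these outcomes are grouped by framing, and an analyst who tried to pair unequal groups would soon notice. Within-group analyses would give each group's mean change, so a difference could be had by subtraction. This is fair, but that difference would still lack a test and an interval, and the wording needs correcting on any reading.

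The disagreement rates in the table describe a rule that the plan never states. This is correct. They show what can go wrong when no between-group test is given and are not error rates of the plan. The inputs are also favorable: complete follow-up is assumed although non-completion is itself an outcome in Section 3.4.4, and the splits borrow from other populations.

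A better test does not make this a clean randomized comparison. Enrollment happens after randomization and is expected to differ by framing, so differences among enrollees may partly reflect who enrolled. This stands, and it applies to a Welch test as much as to an adjusted model. It is a limit on interpretation and does not justify keeping an inapplicable test.

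**Conclusion.** The concern holds. For change in steps and change in symptom scores, the only test named cannot make the comparison promised in Section 3.4.4, and nothing elsewhere in the document supplies one. This is an error in the plan, not an omitted detail, and it depends on no numerical assumption.

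It covers two exploratory measures at two time points, overall and in each of two arms: 2 × 2 × 3 = 12 comparisons. The chi-square analyses of enrollment and attrition suit independent groups and need no change.

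The disagreement rates and interval widths are illustrative. They rest on 100 enrollees with complete data, equal SDs, a two-sided 5% level and the assumed splits. The wide intervals, about ±0.40 to ±0.47 SD overall and ±0.57 to ±0.67 SD within an arm, are a further reason to report the difference with its interval and not p-values alone. The point should be fixed before analysis.

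**What to change.** Replace the paired t test sentence in Section 4 with wording such as:

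> Change in step count and in symptom scores, from baseline to the end of the intervention and to the end of follow-up, will be compared between framing groups using two-sample (Welch) t tests, overall and within each GAME PAD arm, reporting the difference in mean change with a 95% CI. Paired t tests will be used only to describe within-group change.

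Add that these comparisons are exploratory, and that enrollees are a subset formed after randomization, so a difference between framings may reflect who enrolled.

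Optionally, add a model adjusted for baseline value and GAME PAD arm to gain precision. Baseline values among enrollees may differ by framing, so the adjusted result can estimate a different quantity from the change-score comparison, and the plan should say so.

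The cost is a sentence or two of analysis wording. No new data are needed.

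### The exploratory change outcomes are assigned paired t tests with no missing-data method; these do not contrast the framings, and a completers-only comparison could be biased if outcome-related dropout differs by framing

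*Combined protocol and SAP*

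**What the plan says.** Section 3.4.4 (Outcomes) says every outcome will be compared between opt-in and opt-out framing. Three kinds of exploratory outcome are listed for enrolled patients. One is non-completion, given as "the proportion of enrolled patients that failed to complete the study". Another, for steps, is "change in daily step count from baseline to the end of the GAME PAD intervention", with a second time point when follow-up ends. The third is the corresponding change in patient-reported symptom scores. Both change outcomes are to be reported "overall and stratified by overall GAME PAD study arm".

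Section 4 (Statistical Analysis) assigns the methods. Attrition is compared between framings by chi-square: "We will compare the primary outcome and attrition rate between patients initially presented with study participation via opt-in framing versus opt-out framing". For steps, "Change in step count from baseline through the intervention period and follow-up will be compared using paired t tests"; for symptoms, "as will change in patient reported symptom scores from baseline through the intervention period and the end of follow up". The intention-to-treat principle is stated for the primary outcome. For the rest, "Other outcomes, among patients that ultimately enrolled in the GAME PAD study, will similarly group patients by framing of study participation at initial contact".

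The document contains no imputation rule, missing-data assumption, repeated-measures model or sensitivity analysis. It gives no expected dropout rate.

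**The concern.** There are two faults in the same sentence of Section 4.

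The more basic one is the test itself. A paired t test compares two values from the same patient. Opt-in and opt-out enrollees are different people, so pairing can only show whether each group changed from its own baseline. It cannot deliver the between-framing comparison in Section 3.4.4.

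The second remains if a two-sample test is substituted. A change score needs both values, so without another rule an enrollee lacking the later value drops out of the analysis. Section 3.4.4 makes non-completion an outcome, so unequal dropout is an open question in the plan. There is a plausible reason for it: Section 3.4.2 has opt-in patients go to the website themselves, whereas opt-out patients are telephoned unless they decline. If opt-out enrollees are less committed and the poorer responders leave, the remaining opt-out patients look better than the group that enrolled. A reader could then conclude that opt-out recruitment does not cost response when it does.

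**Working it through.** The plan gives no dropout rate, SD, significance level or substudy sample size, so it has no figure to reproduce. Dropout rates, outcome gaps, correlation, dropout strength and the two-sided 5% level below are assumptions.

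**1. Likely group sizes.** Inputs: 100 enrollees (Section 3.1), 3:1 allocation (Section 3.4.1), and earlier enrollment rates of 13% or 16% opt-in against 38% opt-out (Section 1).
- Opt-in share = 3 × 0.13 / (3 × 0.13 + 0.38) = 0.39/0.77 = 0.506, a split of about 51:49.
- With 16%: 0.48/0.86 = 0.558, about 56:44.

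**2. Bias of a completers-only contrast.** Let *d* be the dropout share in a group and *g* the gap in mean change between completers and dropouts, in SD. The completer mean exceeds the mean of all enrollees by *d* × *g*, so

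bias (opt-out minus opt-in) = d_out × g_out − d_in × g_in.

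| Dropout, opt-in vs opt-out | Gap *g* | Bias (SD) |
|---|---|---|
| 10% vs 25% | 0 in both | 0 |
| 10% vs 25% | 0.5 in both | 0.25 × 0.5 − 0.10 × 0.5 = 0.075 |
| 10% vs 30% | 1 in both | 0.30 − 0.10 = 0.20 |
| 10% vs 10% | 0.5 in both | 0 |
| 10% vs 10% | 0 opt-in, 0.5 opt-out | 0.05 |

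Unequal dropout alone is therefore not enough for bias. Equal dropout is not always safe either, if those who leave differ between the groups.

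**3. Simulation with no true framing effect.** Set-up: 51 and 49 enrollees; correlation 0.7 between interim and end change; odds of dropout 2.7 to 4.5 times higher per SD worse interim change. The likelihood estimate regresses end change on interim change among completers in each group and evaluates it at the mean interim change of all enrollees in that group.

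| Dropout | Completers: bias (SD) | Completers: type I error | Likelihood: bias (SD) |
|---|---|---|---|
| 10% vs 20% | about 0.06–0.07 | about 6% | near 0 |
| 10% vs 30% | about 0.11–0.15 | 8–11% | 0.005 or less |
| Either, unrelated to change | 0 | about 5% | 0 |

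The standard error is about 0.21 to 0.22 SD for both methods, so the likelihood estimate costs no precision.

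*Cross-check.* At 10% vs 30% about 46 and 34 completers remain, giving SE = √(1/46 + 1/34) = 0.226. Biases of 0.115 and 0.147 are 0.51 and 0.65 standard errors. The normal approximation then gives type I errors of 8.0% and 10.0%, in line with the simulation.

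**4. When dropout depends on the unseen end value.** With the same rates and odds, the likelihood estimate keeps a bias of about 0.05 to 0.11 SD, against 0.08 to 0.21 SD for completers. It roughly halves the bias but does not remove it.

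**5. Whether the attrition test would give warning.** With 51:49 enrollees, the chi-square test has about 29% power for 10% vs 20% dropout, 51% for 10% vs 25% and 71% for 10% vs 30%. A non-significant result would not rule out differential dropout.

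**The case against.** Much of the case on the other side stands.

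- **Bias is not shown.** A reader might infer from the planned attrition test that dropout will differ and that these comparisons will be biased. Asking the question does not answer it, and bias also needs dropout to be related to change.
- **Completers-only is an inference.** A reader might take it as stated that only patients with both values are kept and that interim data are thrown away. The document says neither. Section 4 speaks of change through the intervention period, Section 3.4.4 of change to its end; an average over a period could use partial data. How steps are captured, and whether leavers' data are retained, is not described. The main GAME PAD protocol is separate, and this document refers to it only for eligibility.
- **Symptom scores gain less.** Only baseline, end of intervention and end of follow-up are documented. Someone who leaves before the end of the intervention has no later score and still contributes nothing to the model. The simulated gain does not carry over.
- **The near-zero likelihood bias is a favourable case.** Dropout there depends only on observed data, the condition under which the method works; step 4 shows what otherwise remains.
- **The outcomes are exploratory and imprecise.** With a standard error of about 0.22 SD, the difference detectable with 80% power is (1.96 + 0.84) × 0.22 ≈ 0.6 SD. A null result could not establish absence of harm under any analysis.
- **No model restores randomization here.** Enrollees are selected by the behaviour that framing is meant to change.

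These points limit the size and certainty of the concern. They do not supply a missing-data method, and they do not make a paired test a between-framing comparison.

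**Conclusion.** The concern holds as a conditional one. The stated test does not give the contrast the plan promises, and the default handling of missing values leaves that contrast open to bias if dropout is related to outcome and acts differently in the two framing groups. The possible size runs from zero to about 0.15 SD in the simulated scenarios where interim change drives dropout, and higher if the unseen end value does. All of this rests on assumed dropout rates and strengths. The documents do not support saying that bias will occur, or that the primary result is at risk: the primary outcome is enrollment, analysed by framing at initial contact. Because the remedy needs only analysis effort, it is worth making even for exploratory outcomes.

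**What to change.** Replace the t tests in Section 4 with one mixed model for repeated measures per outcome, comparing the framings:

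- **Terms:** framing, time, framing-by-time, baseline value and GAME PAD arm. A framing-by-GAME PAD arm term is optional; it would give the stratified estimates from the same model.
- **Data:** every enrollee with a baseline and any later value. For steps, use mean daily steps by period where interim data exist. For symptom scores, state that the gain is limited to baseline adjustment and to patients who have the end-of-intervention value but not the end-of-follow-up value.
- **Assumption and sensitivity:** state that the model removes the bias only if dropout is explained by observed data, and add one sensitivity analysis assuming worse outcomes after dropout.
- **Reporting:** label these results descriptive because enrollees are selected after randomization.

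The cost is plan wording and modest programming, with no new data collection. Before finalizing the step-count model, confirm which interim step data GAME PAD keeps for patients who leave.

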Though opt-out trial participation has increased enrollment in two prior studies, it is uncertain whether it will do the same in a clinical trial intended to promote physical activity in patients with peripheral artery disease (PAD), as these patients differ from those included in the myocardial infarction and diabetes trial in several ways, and the intervention differs as well. We therefore seek to conduct a randomized substudy of the proposed GAME PAD randomized controlled trial, evaluating the effect of opt-out versus opt-in framing of clinical trial enrollment.

2. Study Objectives

The objectives of this study are the following:

1. To determine the effect of an opt-out versus an opt-in approach to enrollment in a clinical trial enrolling patients with peripheral artery disease on the proportion of patients contacted enrolled
2. To determine the effect of an opt-out versus an opt-in approach to enrollment in a clinical trial enrolling patients with peripheral artery disease on the clinical characteristics of patients who decide to enroll in the study

3. Sub-Study Design and Procedures

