3.1 General overview

The GAME PAD study is a two-arm randomized controlled trial aimed at evaluating whether a home-based walking program with automated coaching augmented with gamification and behavioral economic principles improves functional capacity in patients with PAD. The study will randomize 100 patients with PAD to a 16-week home-based walking program using goal-setting alone (attention control) or to the same home-based walking program with automated coaching augmented with gamification and behavioral economic principles. The study will be conducted using the Way to Health platform, and patients will enroll and consent for participation online, with available help from a study coordinator by telephone. This sub-study will test whether opt-in or opt-out framing of study participation upon initial contact affects the proportion of patients who ultimately enroll in the study and the demographic characteristics of enrolled patients.

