3.3. Patient Selection Criteria

Patients are eligible to be included in the study if they are ≥ 18 years of age, have been seen in the University of Pennsylvania Health System, and have an ICD-10 code consistent with peripheral artery disease (I70.2x, I70.3x-I70.7x, I73.9) or peripheral artery disease on their problem list. There are no exclusion criteria.

Please refer to the separate protocol for inclusion and exclusion criteria for the main GAME PAD study.

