3.4.3 Data collection

Baseline characteristics of patients randomized to each framing method will be abstracted from the electronic health record and Penn Data Store, and will include age, sex, race/ethnicity, and medical comorbidities. Whether contacted patients created an account on the Way to Health website and/or ultimately consented for enrollment in the study will be captured.

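### Does comparing attrition, step count and symptoms by framing only among enrollees require a change to the plan?

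*Combined protocol and SAP*

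**What the plan says.** Section 3.4.1 sets the allocation at the email: "Patients will be randomized 3:1 to an email message framing trial participation in a standard opt-in manner", with opt-out framing as the other arm. The primary outcome (Section 3.4.4) is the proportion enrolling, and Section 4 gives its analysis set: "The primary outcome will be analyzed using the intention-to-treat principle, grouping patients by framing of study participation at initial contact".

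The remaining outcomes have a different analysis set. Section 3.4.4 says: "Exploratory outcomes, among patients that ultimately enrolled in the study, will include the proportion of enrolled patients that failed to complete the study", followed by change in daily steps and change in symptom scores. Section 4 adds: "Other outcomes, among patients that ultimately enrolled in the GAME PAD study, will similarly group patients by framing of study participation at initial contact". Attrition is tested by chi-square and the changes by paired t tests.

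The plan also treats the make-up of the enrolled group as something framing may alter. Objective 2 concerns the effect of framing "on the clinical characteristics of patients who decide to enroll in the study", and Section 3.1 asks whether framing "affects the proportion of patients who ultimately enroll in the study and the demographic characteristics of enrolled patients". Section 3.4.3 adds a data item for everyone contacted: "Whether contacted patients created an account on the Way to Health website and/or ultimately consented for enrollment in the study will be captured". Neither Section 3.4.4 nor Section 4 makes account creation an outcome.

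**The concern.** Enrollment happens after randomization and is itself the primary outcome. If opt-out framing brings in people who would not have answered an opt-in email, the two enrolled groups differ in composition, and randomization no longer protects a comparison between them. The plan foresees this in Objective 2, yet it compares attrition, steps and symptoms across those groups without saying that the comparisons are not randomized. Section 4 names the same chi-square test for enrollment and attrition in one sentence. It then uses the word *similarly* for the other outcomes, directly after the intention-to-treat statement. A reader could give an attrition p-value the standing of the enrollment p-value and report that opt-out framing makes people drop out. No listed outcome other than enrollment is defined on all randomized patients, so nothing randomized stands beside the attrition result as a counterweight.

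**Working it through.** The plan states no power, effect size or attrition figure for these outcomes, so there is no figure of its own to reproduce. The check has two parts: how large a selection artifact could be, and whether the plan's use of the comparisons makes it an error.

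**Inputs from the documents.** Allocation 3:1 (Section 3.4.1). 100 patients in GAME PAD (Section 3.1). Enrollment of 13% vs 38% in the diabetes trial and 16% vs 38% in the myocardial infarction trial (Section 1); the second pair was not randomized.

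**Assumptions.** All 100 patients come through these emails. Everyone who would enroll under opt-in would also enroll under opt-out. Framing changes nobody's retention or response. Opt-in attrition is 5%, 10% or 20%. The correlation rho between the propensities to enroll and to stay is 0, 0.3 or 0.5.

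**Enrollee split.** The opt-in share is 3·p_in / (3·p_in + p_out).
- 13%/38%: 0.39 / 0.77 = 0.506, about 51 vs 49.
- 16%/38%: 0.48 / 0.86 = 0.558, about 56 vs 44.

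The share of opt-out enrollees who would also have enrolled under opt-in is 13/38 = 34% or 16/38 = 42%.

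**Attrition.** Enrollment and retention propensities are standard normal with correlation rho. Enrollees are the top 13% (or 16%) under opt-in and the top 38% under opt-out. The dropout threshold is set to give the stated opt-in attrition. Rejection rates are exact binomial for the 5% Pearson chi-square. The three entries in each cell are for opt-in attrition of 5%, 10% and 20%.

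| rho | Opt-out attrition, 13/38 | Rejection, 51 vs 49 | Opt-out attrition, 16/38 | Rejection, 56 vs 44 |
|---|---|---|---|---|
| 0 | 5.0, 10.0, 20.0% | 4.8, 4.8, 5.1% | 5.0, 10.0, 20.0% | 5.2, 5.3, 4.9% |
| 0.3 | 7.5, 14.0, 26.0% | 8.2, 9.1, 11.0% | 7.0, 13.3, 24.9% | 8.4, 8.9, 8.9% |
| 0.5 | 10.2, 18.1, 31.6% | 17.0, 20.6, 26.2% | 9.1, 16.5, 29.5% | 14.7, 17.2, 19.1% |

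Larger contrasts give more. Suppose 10% of those who enroll either way drop out, against 30% or 40% of those who enroll only under opt-out. At 13/38, opt-out attrition is 0.342·10% + 0.658·30% = 23.2%, or 29.7% with 40%. Rejection is then 42% or 71% (37% or 62% at 16/38). With 20% as the base and 44% or 50% in the added enrollees, rejection at 13/38 is 42% or 58%, so ratios of 2.2 and 2.5 suffice there.

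**Step or symptom change.** The gap in enrollee means is rho·[φ(z_in)/p_in − φ(z_out)/p_out], where z is the cut-off for the enrolled fraction. The bracket is 1.627 − 1.002 = 0.625 at 13/38 and 1.521 − 1.002 = 0.519 at 16/38. The gaps are 0.19 and 0.16 SD at rho 0.3, and 0.31 and 0.26 SD at rho 0.5.

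**Would an all-randomized outcome add anything?** The natural candidate is enrolled and completed, with non-enrollees counted as no. At 13/38, 100 enrollees need 100 / (0.75·0.13 + 0.25·0.38) = 519.5 contacts, about 390 vs 130. With 10% opt-in attrition:
- Enrollment: 38.0 − 13.0 = 25.0 points (95% CI 16.0 to 34.0).
- Completers, rho 0: 34.2 − 11.7 = 22.5 points (13.7 to 31.3).
- Completers, rho 0.5: 31.1 − 11.7 = 19.4 points (10.9 to 28.0).

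The difference reaches zero only when opt-out attrition is 1 − 0.13·0.9/0.38 = 69% (62% at 16/38). The measure largely follows enrollment, and it does not measure retention.

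**Is a planned analysis wrong?** Objectives 1 and 2 ask how many enroll and who they are. Neither asks about the effect of framing on an individual's retention or response. For the question of how each recruited cohort goes on to behave, grouping enrollees by framing is the correct analysis, and the rejections above are true detections of cohort differences.

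**The case for a change.** The strongest case for a change is that disclosing an analysis set is not the same as stating what it means. One sentence in Section 4, saying that the enrollee comparisons are not randomized, would cost nothing and would stop a headline about opt-out framing causing dropout. Stratifying by GAME PAD arm does not help, because opt-in versus opt-out within an arm is still not randomized. The facts in this case stand: the restriction, the silence on interpretation, and enrollment as the only listed outcome on all randomized patients.

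The step to a required change does not follow. The sentence that says *similarly* also says that the patients are enrollees, so the analysis set is visible where the misreading would start. The caveat is an interpretation that an analyst can give equally well when reporting; it changes no data, test or estimate. Completers per patient contacted is an optional extra. It does not answer the retention question, and on the figures above it adds little beyond enrollment unless opt-out attrition is very high.

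**Conclusion.** The observation is accurate, but no change follows. The exploratory comparisons are not randomized, and the plan leaves that unsaid. It does disclose the enrollee restriction in both Section 3.4.4 and Section 4, labels the outcomes exploratory and makes no causal claim. The primary intention-to-treat comparison is unaffected.

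The size of a possible misreading is not determined by the documents. It ranges from nothing (5% rejection at rho 0) to 26% at rho 0.5, and higher under steeper assumed attrition contrasts. All of this rests on assumed attrition, correlation and monotone enrollment, on enrollment rates from other populations, and on all 100 patients coming through the emails. It becomes an error only if the report reads the result as an effect of framing on individuals. An experienced analyst would present these results as a description of the recruited cohorts, beside the enrollee characteristics that Objective 2 calls for.
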